12.1 Treatment response variables

Descriptive statistics for body weight (kg), body mass index (kg/m²), waist circumference (WC, cm) and waist to hip ratio (WHR), HbA1c%, fasting blood glucose (mmol/L), lipid profile (cholesterol, triglycerides, LDL, HDL) values together with absolute and relative (%) changes from baseline, as well as systolic and diastolic blood pressure (mmHg) values together with absolute changes, will be tabulated by visit for the FAS population. In addition, descriptive statistics for the above variables and their changes will be tabulated for visits corresponding to Weeks 12, 24, 36, 48, after the imputation of missing values using LOCF approach.

The primary endpoint - the number (proportion) of patients for whom body weight decreased by at least 5% compared to baseline values at 12 months of observation - will be analyzed in FAS (LOCF), additionally the primary endpoint analysis will be repeated in the Per Protocol Set (PP).

The number and proportion of patients with a decrease in body weight of at least 5% compared to the baseline values at 12 months of observation will be tabulated based on available measurements and based on imputed (LOCF) values in the FAS population. The results for the primary endpoint will also be presented by centers.

To compare proportions between groups, the main analysis of the primary endpoint will be carried out using logistic regression with the calculation of the odds ratio with 95% CI. In order to adjust for the potential confounding factors, potentially influencing factors such as age, gender, baseline value of the body mass index, the duration of the disease, baseline level of HbA1c will be included in the regression model.

As part of the sensitivity analysis, the primary endpoint will be analyzed without imputation of missing values using the GEE (Generalized Estimating Equations) method, taking into account the correlation of the repeated measurements at different visits for each patient.

The model will include group, time (visit) and group*time interaction. In addition to group, time and interaction term, only significant influencing factors (age, gender, baseline body mass index, disease duration, baseline HbA1c) ($p < 0.1$) will be included in the model. A first order autoregressive covariance structure [AR (1)] will be used in the model. If convergence is not achieved, other covariance structures (Independent, unstructured covariance structure (Unstructured)) will be tested as possible alternatives. Differences between groups (active group - control group) will be assessed using interaction term group*time, calculating the adjusted means and corresponding 95% confidence intervals for the group*time interaction.

Secondary dichotomous variables - a decrease in body weight by at least 5% at 3, 6, 9 months of observation and at least 10% of the baseline values at 3, 6, 9, 12 months of observation will be analyzed in a similar manner.

Secondary dichotomous endpoints – a decrease of HbA1c level by at least 0.5% from baseline, achievement of HbA1c $\leq 7\%$ by 12 months of observation, a decrease in SBP and DBP by at least 5 mmHg at 3, 6, 9, 12 months of observation - will be analyzed using GEE with the imputation of missing values.

After the imputation of missing values, the endpoints representing the absolute and relative (%) changes in the quantitative variables for 3, 6, 9 and 12 months will be analyzed using the GEE method. The initial values of the relevant variable, age, sex, baseline body mass index, duration of the disease, and the initial value of HbA1c% will be used as factors and covariates. 95% confidence intervals for mean values of the parameters in both groups will be presented, as well as for the difference in the mean values between the compared groups adjusted for the influence of these factors.

In case of significant deviations from the normal distribution (verified using graphical methods), the logarithmic transformation or nonparametric Mann-Whitney U-test will be used as possible alternatives.

All data on primary and secondary endpoints will also be presented in the form of listings.

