12.2 Safety assessment

The safety variables will be analyzed in the Safety Populations, missing measurements will not be imputed.

Adverse events

Adverse events will be coded using the Medical Dictionary for Regulatory Activities (MedDRA, version 19).

Data on adverse events will be presented in terms of the number and proportion of patients with any adverse events overall, by system organ class (SOC) and preferred term (PT).

The number (proportion) of patients with AE and the number of AE will be tabulated by system organ class and preferred term, as well as by relationship to study treatment and severity. Within each system organ class and preferred term, each patient will be counted only once with the closest relationship to the study treatment or maximum severity. In the case of missing value of severity or relationship, the AE will be considered in the table as "severe" and "related", respectively.

The following tables will be provided:

- The number (proportion) of patients with AE and the number of AEs by system organ class and preferred term;
- The number (proportion) of patients with AE and the number of AEs related to study treatment by system organ class and preferred term;
- Number (proportion) of patients with AE and the number of AEs by severity, by system organ class and preferred term;
- The number (proportion) of patients with AE and the number of AEs that led to discontinuation of the program (for the active group), by system organ class and preferred term;
- The number (proportion) of patients with AE and the number of AEs that are fatal, by system organ class and preferred term;
- The number (proportion) of patients with SAE and the number of SAE, by system organ class and preferred term;

The analysis will not include AEs that started before the start of a lifestyle change program for patients in the active group. In the case of a partial start date for AE, it will be compared as far as possible with the program start date to determine if it occurred prior to the start of the program. If the available information is not sufficient, the AE will be considered to have started after the beginning of the program.

The analysis of the SAE will include all registered SAE. Data on all AE / SAE will be presented in the form of listings.

Laboratory data

Laboratory investigations were conducted on Visit 1, Week 12 and 48 and included the following parameters:

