Biochemistry: total protein (g/l), cholesterol, LDL, HDL (mmol/L), triglycerides (mmol/L), ALT (U/l), AST (U/l), CPK (U/l), creatinine ($\mu\text{mol/L}$), GFR.

Haematology: hemoglobin (g/l), leukocytes ($10^9/l$) (+ formula), erythrocytes ($10^{12}/l$), platelets ($10^9/l$), ESR.

Urinalysis: color, transparency, relative density, protein, glucose, ketones.

Descriptive statistics will be used to analyze the laboratory data. Hematology and biochemistry lab parameters values and their absolute changes from baseline will be presented by groups and study visits. Tables of shifts relative to normal ranges (low / normal / high) will be tabulated by visit. For the urinalysis parameters, the number and proportion of the normal / non-clinically significant deviations / clinically significant deviations will be tabulated. All laboratory data will be presented in listings.

Vital signs

Systolic and diastolic pressure (mmHg), heart rate and respiratory rate will be recorded at each visit of the study. For the analysis of vital signs, descriptive statistics will be used. Parameters of blood pressure, heart rate and respiratory rate and their absolute changes in from baseline values will be tabulated by visit. All vital signs data will be presented in listings.

ECG

ECG was performed on Visit 1, Week 12 and 48. The ECG results (normal / non-clinically significant deviations / clinically significant deviations) will be tabulated as the number and percentage of patients with each of the assessments from the number of patients present at the visit.

Physical examination

The results of the physical examination, including an overall assessment of the basic parameters of the vital activity of the organism, will be recorded on Visit 1 and on all visits, beginning from Week 12 in both groups, and also 4 and 8 weeks after inclusion in the study for active group patients. The results of the physical examination will be tabulated as the number and percentage of patients with each of the assessments (normal / non-clinically significant deviations / clinically significant deviations) from the number of patients present at the visit.

13 Other variables

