Table 4.3.5 Analysis of changes in WHR compared to baseline values (FAS)

Table 4.4.1 Descriptive statistics for HbA1c values and their changes in percent and absolute units by study visits (FAS)

Table 4.4.2 Analysis of absolute changes of HbA1c compared to baseline values at 3, 6, 9 and 12 months of observation (FAS)

Table 4.4.3 Analysis of changes in HbA1c in % compared to baseline values at 3, 6, 9 and 12 months of observation (FAS)

Table 4.4.4. Reduction of HbA1c level by at least 0.5% of baseline by study visits (FAS)

Table 4.4.5 Analysis of the reduction in HbA1c level by at least 0.5% from baseline (FAS)

Table 4.4.6 Analysis of the achievement of HbA1c \leq 7% at 12 months of observation (FAS)

Table 4.4.7 Descriptive statistics for FBG values and their changes in percent and absolute units by study visits (FAS)

Table 4.4.8 Analysis of the absolute changes in FBG compared to the baseline values at 3, 6, 9 and 12 months of observation (FAS)

Table 4.4.9 Analysis of FBG changes in % compared to baseline values at 3, 6, 9 and 12 months of observation (FAS)

Table 4.5.1 - 4.5.2 Descriptive statistics for values of SBP and DBP and their changes in absolute units by study visits (FAS)

Table 4.5.3 - 4.5.4 Analysis of absolute changes in SBP and DBP compared to baseline values at 3, 6, 9 and 12 months of observation (FAS)

Table 4.5.6 - 4.5.8 Decrease in SBP and DBP by at least 5 mmHg from baseline (FAS)

Table 4.5.9 - 4.5.10 Analysis of the decrease in SBP and DBP by at least 5 mmHg from baseline by study visits (FAS)

Table 4.6.1 - 4.6.4 Descriptive statistics for lipid profile values (cholesterol, triglycerides, LDL, HDL) and their changes in percent and absolute units for study visits (FAS)

Table 4.7.1 - 4.7.4 Analysis of changes in % of lipid profile (cholesterol, triglycerides, LDL, HDL) compared to baseline values at 3 and 12 months of observation (FAS)

Table 4.8.1 - 4.8.4 Analysis of absolute changes in lipid profile (cholesterol, triglycerides, LDL, HDL) compared to baseline values at 3 and 12 months of observation (FAS)

Table 5.1.1 Frequency table for adverse events (Safety Population)

Table 5.1.2 Frequency table for adverse events by severity (Safety Population)

Table 5.1.3 Frequency table for adverse events by relationship to study treatment (Safety Population)

Table 5.1.4 Frequency table for adverse events leading to discontinuation (Safety Population)

Table 5.1.5 Frequency table for fatal adverse events (Safety Population)

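### SAP 12.1 asks for LOCF lipid summaries at weeks 24 and 36, where the active group has no scheduled lipid test and every value would repeat week 12

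*SAP*

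**What the plan says.** **Descriptive tables.** SAP 12.1 includes "lipid profile (cholesterol, triglycerides, LDL, HDL) values together with absolute and relative (%) changes from baseline" in its list of efficacy variables to be tabulated by visit in the FAS. It then adds a second set of summaries of the same variables and their changes, which "will be tabulated for visits corresponding to Weeks 12, 24, 36, 48, after the imputation of missing values using LOCF approach". Lipids are not excepted.

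**Models.** The same section says that, after imputation, absolute and relative "changes in the quantitative variables for 3, 6, 9 and 12 months will be analyzed using the GEE method". Again lipids are not excepted.

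**Schedule.** SAP 12.2 states: "Laboratory investigations were conducted on Visit 1, Week 12 and 48 and included the following parameters". Cholesterol, LDL, HDL and triglycerides are named in the biochemistry panel that follows, and the two groups are not distinguished. Protocol Amendment 1 describes the same timing for blood chemistry. Protocol Table 7-1 (active group) has three marks in the clinical chemistry row, and its footnote 5 puts the lipids in that panel.

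**Control group.** Protocol section 10 says something different. To supply the primary and secondary endpoints, which include lipids, all indicators are to be assessed in controls at the start and at the end of months 3, 6, 9 and 12. It refers to Table 7-2, which is not in the text available for this review.

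**Table list.** SAP 18.1 describes the lipid model tables (4.7.1-4.7.4 and 4.8.1-4.8.4) as changes "compared to baseline values at 3 and 12 months of observation (FAS". The lipid descriptive tables (4.6.1-4.6.4) are listed by study visit with no limit on weeks.

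**The concern.** LOCF is meant to fill in a measurement that was due and not obtained. The rule in SAP section 8 carries the last value after the start of the programme or observation. It does not separate a missed measurement from one that was never planned. Applied to lipids at weeks 24 and 36, it fills a whole column of the table rather than a few gaps.

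Lipid change is a listed secondary endpoint, and the stated purpose includes showing that weight loss improves lipid metabolism. A table with lipid changes at weeks 12, 24, 36 and 48 looks like evidence that an early change lasted through the middle of the year. In the active group nobody would have observed that.

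The model text raises the same problem. If an analyst followed it rather than the table list, adjusted group differences with confidence intervals would be reported at months 6 and 9 with no active-group lipid data from those months.

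**Working it through.** The documents state no figure to reproduce here, so the check sets schedule, imputation rule and requested output side by side.

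**1. Put months and weeks on one scale.** The SAP takes 1 month as 4 weeks, so months 3, 6, 9 and 12 are weeks 12, 24, 36 and 48.

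**2. Compare schedule with output for lipids.**

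| Week | Active: lipids scheduled (SAP 12.2, Table 7-1) | Control: SAP 12.2 | Control: Protocol section 10 | LOCF table (SAP 12.1) | GEE text (SAP 12.1) | Lipid model tables (SAP 18.1) |
|---|---|---|---|---|---|---|
| 12 | yes | yes | yes | yes | yes | yes |
| 24 | no | no | yes | yes | yes | no |
| 36 | no | no | yes | yes | yes | no |
| 48 | yes | yes | yes | yes | yes | yes |

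**3. Apply the LOCF rule.** Baseline is not carried forward, so the only scheduled value available at week 24 or 36 in the active group is the one from week 12. A patient with a week-12 value receives it at both later weeks, and a patient without one stays missing. The rows for weeks 24 and 36 therefore have the same n, mean and individual values as week 12.

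**4. Confirm by simulation.** Inputs were 100 active and 30 control patients and 20% active dropout with none in control (SAP section 6). Assumptions were 5% sporadic missingness and lipid values drawn with mean 5 and SD 1.
- SAP 12.2 schedule, active: observed n at weeks 12, 24, 36, 48 = 95, 0, 0, 77; n after LOCF = 95, 95, 95, 99; mean after LOCF = 4.8728, 4.8728, 4.8728, 4.847.
- SAP 12.2 schedule, control: observed n = 29, 0, 0, 30; after LOCF, weeks 24 and 36 again equal week 12 exactly.
- Protocol section 10 schedule, control: observed n = 29, 27, 30, 29; weeks 24 and 36 differ from week 12. Active weeks 24 and 36 are still exact copies.

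The assumed values do not affect the identity of the rows, which follows from step 3.

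**5. Count the affected cells** (one lipid, one visit, one group).
- Active group, under either control schedule: 4 lipids x 2 visits = 8 cells, covering 100/130 = 77% of planned patients.
- Both groups, if SAP 12.2 also governs controls: 4 x 2 x 2 = 16 cells.
- If Protocol section 10 governs controls: 8 cells are wholly carried forward and 8 are mostly observed. Weeks 24 and 36 would then set carried-forward active values against observed control values.

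**The case against.** The strongest reply is that the SAP's authors already knew the lipid schedule. All eight lipid model tables stop at months 3 and 12, whereas the corresponding weight, HbA1c, glucose and blood pressure model tables run through 3, 6, 9 and 12. A specific output list is a fair guide to intent when the methods text is generic. The by-visit tables without imputation would also show that the active group has no lipid data at weeks 24 and 36, so an attentive reader would be warned. Both arguments stand, and they keep the point small. They do not remove it: Tables 4.6.x carry no such limit, and the text and the list still disagree about the models.

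Three stronger readings are tempting and are not supported.

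- A reader might infer that lipids are never measured at weeks 24 and 36 in anyone, so that all 16 cells are wholly imputed. Protocol section 10 says otherwise for controls. Only the 8 active-group cells are secure.
- A reader might infer that half the values entering the lipid models would be copies. That requires following the generic text against the table list, which does not plan those visits for lipids.
- A reader might infer that the copied visits would shrink the GEE standard errors. The SAP does not say which type of standard error is used, and GEE treats visits as clustered within patient. In a simulation with 100 and 30 patients, robust errors and an assumed within-patient correlation of about 0.5, the standard error of the group difference at weeks 12 and 48 was 0.204 with two real visits. It was also 0.204 with four visits of which two were copies, under independence or AR(1). A clear fall, from about 0.145 to 0.10, appeared only for a single pooled group effect with an independence structure and model-based errors. That agrees with hand arithmetic at unit SD: sqrt(1/100 + 1/30) = 0.208, then 0.208/sqrt(2) = 0.147 and 0.208/sqrt(4) = 0.104. The SAP asks for group differences by time point, so this case cannot be presumed.

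**Conclusion.** The rule is wrong as written. Followed literally, SAP 12.1 produces active-group lipid rows at weeks 24 and 36 that contain nothing but week-12 values: 8 summary cells covering 100 of 130 planned patients. This rests on the schedule in SAP 12.2, which Amendment 1 and Table 7-1 support, and on there being no unscheduled lipid tests.

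For the control group the documents conflict. Under SAP 12.2 the control rows are copies too. Under Protocol section 10 they hold observed values, and the comparison at those weeks mixes carried-forward with measured data. Neither reading gives a usable group comparison at weeks 24 and 36.

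The GEE wording and the lipid model tables contradict each other about months 6 and 9. The harm would be estimates at time points without active-group data; no loss of validity at weeks 12 and 48 has been shown. The primary endpoint is untouched, and the whole matter is a minor correction to secondary-endpoint output.

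**What to change.** In SAP 12.1:

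- limit the lipid LOCF summaries and the between-group lipid models to weeks 12 and 48, in line with Tables 4.7.x and 4.8.x;
- state that LOCF is not applied at a visit where the variable is not scheduled;
- give Tables 4.6.x the same limit for their imputed rows.

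Reconcile the control-group lipid schedule between Protocol section 10, Table 7-2 and SAP 12.2. If controls do have lipid values at weeks 24 and 36, report them by visit without imputation, so that restricting the comparison does not discard observed data.

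The cost is a sentence or two in the SAP and one check of the control schedule. No new data are needed, and the output becomes shorter.

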- 1) Structured modified diet change;
- 2) Balanced and personalized physical exercises;
- 3) Cognitive behavioral support;
- 4) Intensive interactive medical assistance;
- 5) Group education.

The total duration of the study for each patient is 12 months (1 month is equal to 4 weeks or 28 days). Patients from active group will be monitored intensively during the first three months (weekly, with allowed visit window of +/- 1 day) and then will continue to participate in the study for the remaining 9 months. After the first 13 weeks, monthly (+/- 3 days) assessments of weight and health status of patients from the active group will be performed. Key laboratory parameters will be measured and the physician will make a decision on whether the diabetes therapy should be adjusted as the patient's weight is reduced.

3 Sample size determination

The primary objective of this study is to assess the change of weight from baseline, in patients with T2DM at 12 months in comparison to the change in weight from baseline in the parallel cohort. Sample size was calculated based on weight changes observed in Why Wait study conducted at the Joslin center. The average weight loss observed at the end of 12 months was 8%. Given that baseline criteria and translation of the program can be different in its implementation in Russia, we have assumed an achievable change in weight as 5%. Significant reduction of body weight in the control group is not anticipated. The sample size (with the possible dropout of 20%) of 100 patients in active group and 30 patients in parallel cohort is sufficient to provide 80% power to detect a significant difference (significance level is $\alpha=0.05$) between values in the two groups.

4 Randomization and blinding

Not applicable.

5 Efficacy assessment

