5.2 Secondary endpoints

- Body weight decrease expressed in percents and in absolute values in comparison with baseline at 3, 6, 9, 12 months of observation;
- Number (proportion) of patients achieved weight loss of at least 5% in comparison with baseline at 3, 6, 9 months of observation;
- Number (proportion) of patients achieved weight loss of at least 10% in comparison with baseline at 3, 6, 9, 12 months of observation;
- Changes of HbA1c and FPG levels expressed in percents and in absolute values;
- Number (proportion) of patients achieved decrease of HbA1c by at least 0.5% in comparison with baseline;
- Number (proportion) of patients achieved HbA1c $\leq 7\%$ at 12 months of observation;
- Blood pressure changes in absolute values in comparison with baseline;
- Number (proportion) of patients achieved decreasing of systolic and diastolic blood pressure levels by at least 5 mmHg in comparison with baseline;
- Changes of lipid profile (cholesterol, triglycerides, LDL, HDL) expressed in percents and in absolute values in comparison with baseline;
- Changes of waist circumference, waist-to-hip ratio;
- Changes of BMI;
- Assessment of changes by Hypoglycemia Perspectives Questionnaire for active group patients, as well as by perceived exertion rate with Borg scale.

6 Patients enrolled in the study

The study planned to include 130 patients with type 2 diabetes and obesity. In the active group, it was planned to recruit 100 patients, who will actively participate in lifestyle correction program; the control group will consist of 30 patients with T2DM, matching the active group patients by main parameters, who will to be managed in accordance with routine clinical practice for T2DM patients. The control group should be comparable to the active group with regard to the core baseline parameters.

When forming the control group, the following criteria should be taken into account (inclusion criteria in the study): BMI (<30 ; ≥ 30) and baseline HbA1c (<7.5 ; ≥ 7.5). The decision about inclusion of a patient in the active or control group is left at the discretion of the treating physician.

Dropout of 20% from initially enrolled population was considered by the study design. The patient's dropout from the study is defined as three consecutively missed classes within the first 12 weeks of observation in the active group. No dropout in the control group is assumed.

Patients are distributed between two sites participating in the study.

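### With 30 controls, the odds ratio for at least 10% weight loss may have no finite estimate at one or more visits, and the SAP's only fallback does not deal with this

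*SAP*

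**What the plan says.** SAP section 12.1 sets the method for the primary endpoint (loss of at least 5% at 12 months): "the main analysis of the primary endpoint will be carried out using logistic regression", giving an odds ratio with 95% CI. The model contains group plus age, sex, baseline BMI, disease duration and baseline HbA1c. A sensitivity analysis uses GEE on the repeated binary outcome with group, visit and their interaction.

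The secondary weight responders follow the same route. The 5% endpoint at the earlier visits and a loss of "at least 10% of the baseline values at 3, 6, 9, 12 months of observation will be analyzed in a similar manner".

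On numbers, SAP section 6 says "the control group will consist of 30 patients with T2DM" and "No dropout in the control group is assumed". SAP section 3 adds "Significant reduction of body weight in the control group is not anticipated".

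Section 12.1 has two contingency rules. One is for the GEE: "If convergence is not achieved, other covariance structures" are tried. The other, a log transformation or Mann-Whitney test, is for non-normal quantitative variables and cannot apply to a binary endpoint. The SAP names no penalised or exact method, no risk difference, and no rule for a group without responders.

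**The concern.** Losing 10% of body weight is a demanding threshold for 30 patients in routine care whose average weight is not expected to fall much. An empty control cell at one or more of the four visits is therefore a realistic outcome. The planned model then has nothing finite to estimate. Software stops at an arbitrary large value and prints a standard error that means nothing, or it fails.

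Without a rule written in advance, the analyst chooses a replacement method after seeing the empty cell, in an open, non-randomised study. There is a further risk: the GEE fallback is triggered by non-convergence, and a program may report convergence on a divergent estimate. A meaningless odds ratio with a narrow interval could then go into the tables.

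**Working it through.** **Inputs.** From the SAP: 100 active and 30 control patients, 20% dropout, none assumed among controls, a 5% weight change, 80% power and alpha 0.05. Not given in either document: the SD of percentage weight change and the control response rate. Assumed here: normally distributed control change with mean 0, a range of SDs, and a two-sided test.

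**1. The plan's own figure.** SAP section 3 says of "The sample size (with the possible dropout of 20%) of 100 patients in active group and 30 patients in parallel cohort" that it gives 80% power, and on the effect "we have assumed an achievable change in weight as 5" per cent. This cannot be reproduced without an SD, but it can be solved for one. For a comparison of means:

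SD = 5 × √[n₁n₂/(n₁+n₂)] / (1.960 + 0.842)

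- 100:30 gives 5 × 4.804 / 2.802 = 8.57
- 80:30 gives 5 × 4.671 / 2.802 = 8.34
- 80:24 gives 5 × 4.297 / 2.802 = 7.67

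The stated power thus fits an SD of about 8.3 to 8.6 if only active patients drop out. At SD 5 the power with 80:30 would be 99.7%.

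**2. Chance of no control responder at one visit.** Control rate p = 1 − Φ(threshold/SD), and P(0 of 30) = (1 − p)³⁰. Example, 10% threshold at SD 5: p = 1 − Φ(2) = 0.0228, and 0.9772³⁰ = 0.50.

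| SD | p, ≥10% | P(0/30), ≥10% | p, ≥5% | P(0/30), ≥5% |
|---|---|---|---|---|
| 3 | 0.04% | 99% | 4.8% | 23% |
| 4 | 0.6% | 83% | 10.6% | 3.5% |
| 5 | 2.3% | 50% | 15.9% | 0.6% |
| 6 | 4.8% | 23% | 20.2% | 0.1% |
| 8 | 10.6% | about 4% | 26.6% | <0.1% |
| 8.4 | 11.7% | about 2% | 27.6% | <0.1% |

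If controls lose 1 point on average, the 10% column falls to 69%, 33%, 13% and 1% at SD 4, 5, 6 and 8.4.

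**3. Any of the four visits.** Simulating the four visits with the same SD at each and an AR(1) correlation of 0.8, the chance of at least one empty control cell for the 10% endpoint is 98% at SD 4, 83% at SD 5, 53% at SD 6 and 8% at SD 8.4.

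**4. What the models do with an empty cell.** Take active as the reference group. The group coefficient then enters only the control patients' terms. If all are non-responders, the likelihood keeps rising as that coefficient goes to minus infinity, whatever the covariates. A simulated data set with 10 of 100 active and 0 of 30 control responders shows this:

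- Ordinary logistic regression, group plus five covariates: log odds ratio 4.0, 9.1, 19.1 and 29.1 after 5, 10, 20 and 30 iterations, with the standard error rising from 3.7 to about 976,000.
- Firth-penalised fit to the same data: log odds ratio 2.02 (SE 1.39), odds ratio about 7.5.

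The working covariance in a GEE does not alter the mean model, so changing it cannot make an empty cell's log odds finite. With control responders of 2, 2, 1 and 0 over the visits, and 19, 17, 17 and 16 of 100 in the active group, the 12-month log odds ratio ran to about 24 under independence and 30 under AR(1) and unstructured. The SE was 0.27 in the first case and undefined in the other two. All three fits were flagged as converged. This was not run in SPSS, the SAP's software.

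**5. Bias when the estimate is finite.** Simulations with 100 v 30, a 45% active rate and group plus five covariates gave a maximum-likelihood bias of about +0.15 in the log odds ratio at control rates of 10% to 16% (individual runs up to +0.19). The true values are 2.00 at 10% and 1.46 at 16%. Coverage of the 95% Wald interval was about 97%. At a control rate of about 28% the bias was only +0.05 to +0.07.

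**The case against.** The strongest reply is that the high probabilities conflict with the plan's own power. SDs of 3 to 5 would mean power of at least 99.7% at 80:30. At the SD that fits 80%, an empty cell for the 10% endpoint has a chance of about 2% at one visit and 8% over four. This stands as a limit on size. It does not settle the matter, because the SAP states no SD and the back-solved value may not be what the sponsor used. Even at SD 8.4 only 30 × 0.117 = 3.5 control responders are expected, against a group term and five covariates.

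A reader might infer that the primary analysis is likely to fail. The documents do not support that. The SAP says that a significant reduction is not anticipated in controls, which is most naturally a statement about the group's average. It does not say that no control will lose weight, and a zero mean does not imply zero responders. A 5% control rate on the primary endpoint, with a 21% chance of an empty cell (0.95³⁰), would need an SD of about 3.

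A reader might also infer that small-sample bias invalidates the primary result. At about a quarter of the estimate's sampling SD (0.63 to 0.66 in simulation), with coverage at or above nominal, it does not.

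Nor would the study be left without usable weight results. The SAP tabulates responder counts by visit, where 0 of 30 can be read directly, and it models mean weight change with adjusted group differences, which empty cells do not affect. The SAP also does not specify a Wald interval. The gap is in the adjusted odds ratio, chiefly for the 10% endpoint.

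**Conclusion.** The point holds for the 10% weight-loss endpoint. With unpenalised logistic and GEE-logistic models (the ordinary reading of the SAP's wording) and 30 controls, an empty control cell leaves the planned odds ratio without a finite estimate, and no stated rule handles it. The size depends on an SD that the documents do not give. With zero mean control change, the chance at one visit runs from 83% at SD 4 through 50% at SD 5 and 23% at SD 6 to about 2% at SD 8.4.

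For the 5% primary endpoint the risk is small: 23% at SD 3, 3.5% at SD 4 and under 1% from SD 5 upward. The bias there is modest. A pre-specified fallback is enough for it, and a new primary method is not needed. The change should be made before database lock, since it is cheap and otherwise the choice would be made after seeing the data.

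**What to change.** In SAP section 12.1:

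- **10% endpoint, each visit:** use Firth-penalised logistic regression with a profile-likelihood 95% CI and the same five covariates.
- **5% endpoints, including the primary:** keep ordinary logistic regression, and name the same Firth model as the fallback if either group has no responders or very few. State the numerical threshold in the SAP.
- **GEE:** state that no GEE odds ratio will be reported for a visit at which a group has an empty cell. Fitting Firth models visit by visit does not repair the GEE, and a convergence flag must not serve as the trigger.
- **Support:** add the risk difference with a Newcombe 95% CI, labelled as unadjusted. Because the physician chooses the group, it cannot replace the adjusted comparison.

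The cost is SAP wording, and possibly an SPSS extension or other software for the Firth fit. The odds ratio is also pulled towards 1, noticeably so when control responders are very rare. At a 10% control rate, the Firth bias averaged about +0.03 over all simulated trials but −0.08 among those where the ordinary estimate was finite. The report should say that the estimate is penalised.
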